### **3.3 Study Population**

#### **3.3.1 Patient Population**

The patient population in this study will be hyperuricemic (SUA > 6 mg/dL) adult men and women (age  $\geq$  18) diagnosed with chronic gout and who are refractory to conventional therapy. Gout refractory to conventional therapy occurs in patients who have failed to normalize SUA and whose signs and symptoms are inadequately controlled with xanthine oxidase inhibitors at the

maximum medically appropriate dose or for whom these drugs are contraindicated. To enter this study, the patient and the physician must have decided to begin treatment with KRYSTEXXA.

The sample size for the study will be approximately 500 patients treated for one year. This sample size is a pragmatic one that will allow enough patients to enroll in a suitable time period for evaluation of the frequency and severity of IRs, anaphylaxis and immune complex-related AEs and to identify SAEs associated with KRYSTEXXA therapy in this post-approval, observational study.

### **3.3.2 Inclusion and Exclusion Criteria**

#### **3.3.2.1 Inclusion Criteria**

Patients are eligible for the study if all of the following apply:

- Adult patients (age  $\geq$  18 years) with chronic gout refractory to conventional therapy, defined as patients who have failed to normalize SUA and whose signs and symptoms are inadequately controlled with xanthine oxidase inhibitors at the maximum medically appropriate dose, or for whom these drugs are contraindicated.
- Patients who have made the decision, along with their treating physician, to begin treatment with KRYSTEXXA.
- Patients who are willing and able to give informed consent and adhere to visit/protocol schedules (informed consent must be given before the first study procedure is performed).

#### **3.3.2.2 Exclusion Criteria**

Patients will be excluded from participation in the study if any of the following apply:

- Glucose-6-phosphate dehydrogenase (G6PD) deficiency
- Non-compensated congestive heart failure
- Pregnancy or breast feeding
- Prior treatment with pegloticase or another recombinant uricase
- Known allergy to urate oxidase
- Prior treatment or concomitant therapy with a polyethylene glycol (PEG)-conjugated drug
- Recipient of an investigational drug within 4 weeks prior to study drug administration or plans to take an investigational agent during the study

### **3.4 Treatments**

#### **3.4.1 Investigational Drug and Reference Therapy**

##### **3.4.1.1 Investigational Drug**

No investigational drug will be utilized in this post-market, observational study.

### **3.4.1.2 Reference therapy**

KRYSTEXXA is commercially available in the US as a sterile, clear, colorless solution containing 8 mg/mL pegloticase in phosphate-buffered saline. KRYSTEXXA® (pegloticase) concentrations are expressed as concentrations of uricase protein. Each mL of KRYSTEXXA contains 8 mg of uricase protein conjugated to 24 mg of 10 kDa monomethoxypoly(ethylene glycol) (mPEG). Excipients include disodium hydrogen phosphate dihydrate, sodium chloride, sodium dihydrogen phosphate dihydrate and water for injection.

KRYSTEXXA is supplied in a single-use, 2 mL glass vial with a Teflon coated (latex-free) rubber injection stopper to deliver KRYSTEXXA as 8 mg of uricase protein in 1 mL volume for i.v. infusion. Before preparation for use, KRYSTEXXA should be stored in the carton, maintained under refrigeration between 2°C and 8°C (36°F and 46°F), protected from light and should not be shaken or frozen.

### **3.4.2 Treatment Assignment**

All patients will receive KRYSTEXXA 8 mg by i.v. infusion every 2 weeks.

### **3.4.3 Blinding**

This is an open-label study.

### **3.4.4 Treatment Compliance**

All doses of KRYSTEXXA will be administered in a healthcare setting by healthcare professionals. The number of doses and amount of each dose received by each patient will be captured in the patient's medical record and in the case report form (CRF)/electronic case report form (eCRF).

### **3.4.5 Concomitant Therapy**

Pharmaceutical agents specifically indicated for lowering SUA (e.g., allopurinol) should not be used in conjunction with KRYSTEXXA. KRYSTEXXA is indicated for use in patients with chronic gout whose signs and symptoms are inadequately controlled with conventional therapy (i.e., xanthine oxidase inhibitors such as allopurinol). If a patient is being followed after discontinuation of KRYSTEXXA (see Section 3.5.3), another urate-lowering drug may be instituted at any time.

All medications taken for concurrent medical conditions and any required analgesics must be recorded in patients' medical records and in the CRF/eCRF. Data captured on the use of concomitant medications will include the name of the drug, and if known, the start date, stop date and indication.

The use of all other investigational drugs is prohibited throughout the study.

## **3.5 Visit Schedules and Assessments**

The schedule of visits and assessments can be found in Appendix 3.

### **3.5.1 Screening Procedures**

Prior to entry into the protocol, the nature and risks of the study must be reviewed with each patient. Each patient or each patient's legal representative must be given the opportunity to read the Institutional Review Board's (IRB) approved informed consent (IC) form and ask questions. After all questions raised by a potential participant are answered, and before any protocol-specified screening procedures are initiated, each patient or each patient's legal representative must sign and date the consent form. A copy of the signed and dated IC form must be provided to the patient.

After IC is obtained, a 6-digit patient number will be assigned. The first three digits of each patient number will represent the site and the last three will be unique for each patient at each site. Potential patients will be screened to determine if they satisfy all inclusion and exclusion criteria. All screening procedures must be completed prior to dosing. Specified CRF/eCRF pages to report basic demographic information and reason(s) for exclusion must be completed for all patients who signed an informed consent form, but never received KRYSTEXXA.

The following evaluations will be performed on each patient and results recorded in the medical record and CRF/eCRF:

- Informed consent (process must be documented in the medical record)
- Medical history – include all clinically significant medical problems within the past 5 years, but excluding gout history which will be separately documented
- Gout history and symptom severity
  - Documentation of the contraindication to or the failure of conventional therapy at the maximum medically appropriate dose
  - Number of gout flares in the last 6 months, and most recent occurrence
  - Assessment of tophi and gouty arthritis, including a count of the total number of palpable subcutaneous and subperiosteal tophi, if accessible
  - The number of tender joints and swollen joints
  - Documentation of the history of gout-related kidney disease
- Physical examination (including but not limited to dermatological, head and neck, chest and cardiac, abdominal, musculoskeletal, and nervous system examination)
- Vital signs and height and body weight
- Obtain a blood sample for analysis of SUA
- Obtain a blood sample for G6PD testing

- Review concomitant medications
- Initiate gout flare prophylaxis and advise patient to contact site within 12 hours of gout flare symptom onset. If prophylaxis is contraindicated, document the reason.
- Advise patient of the IR prophylaxis regimen to be used before each scheduled KRYSTEXXA infusion.

### **3.5.2 Study Procedures**

#### **3.5.2.1 Visits 1 through 26**

At each visit, the following procedures must be completed **before administration of KRYSTEXXA**:

- Provide the KRYSTEXXA Medication Guide and answer any questions the patient has.
- Review concomitant medications, and question patient about any new medical conditions.
- Record all new clinically significant medical conditions in both the medical record and on the adverse event CRF/eCRF and evaluate for the occurrence of an acute gout flare since the previous visit.
- After the first visit, serum uric acid (SUA) levels will be monitored prior to the next infusion and therapy will be discontinued if levels increase above 6 mg/dL on two consecutive measurements. If the SUA is noted to be above 6 mg/dL the sponsor suggests that a repeat SUA should be drawn when the result is noted to confirm, and if the 2 consecutive levels are noted to be above 6 mg/dL then it is advised to discontinue therapy.
- Record blood pressure, heart rate, respiratory rate and temperature shortly before study drug infusion.
- If patient has not had SUA analyzed between his/her last visit and the current one, obtain blood samples for analysis of SUA.
- Record self-administered pre-medications the patient took for prophylaxis against infusion reactions, and administer hydrocortisone (see Section 3.5.8). Record the drug name, dose, route and time of administration of each medication.

**At Visit 1**, but not routinely for other visits, also obtain blood samples for baseline determination of complement components (C3, C4), tryptase level, and identification of antibodies to pegloticase or PEG. These baseline samples will be stored for later analysis to compare with blood samples that are collected at subsequent visits to assess these parameters as part of the evaluation of an IR or potential immune-complex related event (see Section 3.5.8.3).

Following completion of the above procedures:

- Administer KRYSTEXXA (admixed in 250 mL 0.45% or 0.9% Sodium Chloride Injection, USP) by i.v. infusion over 120 minutes. Record the infusion start and finish times, and total volume infused. Details regarding study drug preparation and administration can be found in Section 7.2 and are described in the FDA-approved KRYSTEXXA Full Prescribing Information.
- Follow standard procedures at the center at which the infusion is being performed to monitor for IRs.
- Monitor for AEs during the infusion. See Section 3.5.8 for management and documentation of possible infusion-related reactions.
- Patients may be discharged after an appropriate period of time for post-infusion observation (approximately 1 hour after completion of the infusion is recommended).
- Monitor therapy by providing the patient with a laboratory slip and advising him/her to have blood drawn for analysis of SUA prior to the next dosing visit.

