A retrospective analysis of the data from the Phase 3 trials revealed that most IRs occurred when uric acid values were above 6 mg/dL. Importantly, other than one case that met the criteria for anaphylaxis occurring during the first dose of pegloticase (8 mg), all other cases that met the criteria for anaphylaxis occurred when a subject's last uric acid value was above 6 mg/dL. Thus, the monitoring rule was developed and incorporated into the FDA-approved Full Prescribing Information:

“Monitor serum uric acid levels prior to infusions and consider discontinuing treatment if levels increase to above 6 mg/dL, particularly when 2 consecutive levels above 6 mg/dL are observed.”

Other non-serious AEs reported in  $\geq 5\%$  of patients treated with KRYSTEXXA 8 mg every 2 weeks included nausea (12%), contusion or ecchymosis (11%), nasopharyngitis (7%), constipation (6%), chest pain (6%) and vomiting (5%).

Anti-pegloticase antibodies developed in 92% of patients treated with KRYSTEXXA. High anti-pegloticase antibody titers ( $> 1:2430$ ) were associated with both a failure to maintain pegloticase-induced normalization of uric acid and a higher incidence of IRs. Because of this high rate of antibody development, one of the specific safety endpoints in the larger population for the current study will be to determine if there is a risk of immune complex disease in patients treated with KRYSTEXXA. No cases of immune complex disease were identified in the pre-marketing controlled clinical studies.

While KRYSTEXXA has not been formally studied in patients with congestive heart failure, there were some patients who experienced exacerbation during the clinical studies. It was

therefore recommended that treating physicians exercise caution when using KRYSTEXXA in patients who have congestive heart failure and to monitor patients closely following infusion.

Glucose-6-phosphate dehydrogenase (G6PD) deficiency is a contraindication for KRYSTEXXA due to the risk of hemolysis and methemoglobinemia in these patients. Therefore, all patients in this study must be screened for this enzyme deficiency.

Refer to the current version of the FDA-approved KRYSTEXXA Full Prescribing Information and Pegloticase Investigators Brochure for detailed information concerning the safety profile of KRYSTEXXA.

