In addition, post-hoc analyses of the clinical study data demonstrated that if KRYSTEXXA had been stopped when a patient's uric acid level rose to greater than 6 mg/dL at 2 consecutive visits, the incidence of IRs would have been reduced by half and there would have been little change in the efficacy outcome. Current guidance for the use of KRYSTEXXA thus recommends monitoring SUA levels prior to infusions and considering discontinuing treatment if SUA levels increase to above 6 mg/dL, particularly when 2 consecutive levels above 6 mg/dL are observed. This study will follow this guidance and provides for the collection of data on both SUA levels and IRs to extend the knowledge base regarding the relationship between these factors.

The design of this study follows the FDA-approved Full Prescribing Information for the use of KRYSTEXXA and allows for capturing additional data related to the safety and efficacy of KRYSTEXXA within the standard healthcare setting. Efforts have been made to limit study-specific activities for the enrolled patients and participating healthcare providers while still allowing for a robust assessment of key safety and efficacy features of KRYSTEXXA treatment in this patient population.

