### **3.5.5 Interruption of Treatment**

Dosing with KRYSTEXXA may be delayed or interrupted for example, for vacation or for intercurrent illness, without requiring a patient to be discontinued from the study. The reason for the delay or interruption will be captured in both the medical record and the CRF/eCRF. If the SUA is  $>6$  mg/dL after an interruption in treatment, the patient may still resume treatment.

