## 7.2.2 Dose Administration

### **Do not administer as an intravenous push or bolus.**

Monitoring Therapy: The risk of anaphylaxis and IRs is higher in patients who have lost therapeutic response. Serum uric acid (SUA) levels will be monitored prior to infusion and therapy will be discontinued if levels increase above 6 mg/dL on two consecutive measurements. If the SUA is noted to be above 6 mg/dL the sponsor suggests that a repeat SUA should be drawn when the result is noted to confirm, and if the 2 consecutive levels are noted to be above 6 mg/dL then it is advised to discontinue therapy.

The KRYSTEXXA admixture should only be administered by i.v. infusion over no less than 120 minutes via gravity feed, syringe-type pump, or infusion pump. Patients should receive pre-infusion medications (antihistamines and corticosteroids) to minimize the risk of anaphylaxis and IRs. Administer KRYSTEXXA in a healthcare setting and by healthcare providers prepared to manage anaphylaxis and IRs, and observe patients for an appropriate period of time after administration.

Refer to the KRYSTEXXA Full Prescribing Information for management of an IR. Since IRs can occur after completion of the infusion, observation of patients for approximately an hour post-infusion is recommended.

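### The SAP counts as protocol violations some SUA draws and dosing delays that the protocol directs or permits, and no SAP item relates infusion reactions to SUA level

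*Protocol*

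**What the plan says.** **Stopping rule.** Section 3.5.2.1 says that "therapy will be discontinued if levels increase above 6 mg/dL on two consecutive measurements", and in the next sentence that "if the 2 consecutive levels are noted to be above 6 mg/dL then it is advised to discontinue therapy". The Synopsis and Section 7.2.2 repeat both sentences. Section 3.2 says the study follows the label guidance, which it gives as "considering discontinuing treatment if SUA levels increase to above 6 mg/dL, particularly when 2 consecutive levels above 6 mg/dL are observed".

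**When SUA is drawn.** Section 3.6.1 asks for blood several days before each infusion. Section 3.5.2.1 sends the patient away with a laboratory slip for a draw before the next visit, and provides a fallback: "If patient has not had SUA analyzed between his/her last visit and the current one, obtain blood samples for analysis of SUA". The protocol contains no 48-hour limit.

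**When doses are given.** Infusions are planned every 2 weeks, but Section 3.5.5 says "Dosing with KRYSTEXXA may be delayed or interrupted for example, for vacation or for intercurrent illness" without removing the patient from the study. A patient whose SUA is above 6 mg/dL after an interruption may resume. Appendix 3 lists infusion visits by week with no tolerance.

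**What the SAP tabulates.** Under Report Format/Structure:
- Items 3 and 4 are both headed as protocol violations.
- Item 3b counts patients infused after two consecutive values above 6.
- Item 3c counts patients with an SUA sample taken more than 48 hours before infusion who had an AE or SAE.
- Item 4 covers any schedule that is not two-weekly. Its only line, 4a, counts such patients who had an AE or SAE.

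**Why SUA and IRs are collected together.** Section 3.2 says the study "provides for the collection of data on both SUA levels and IRs to extend the knowledge base regarding the relationship between these factors".

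**The concern.** Items 3c and 4a pair a violation label with IRs, anaphylaxis and other adverse events. A reader of the report will take those cells as events that occurred where sites departed from the protocol. If the label also falls on patients sampled or dosed as the protocol allows, the cells invite the wrong explanation for the events in them.

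The missing table matters because of the hypothesis in Section 6.1.6, which credits SUA monitoring and stopping with a lower IR rate than in Phase 3. Section 1.2.2 reports that "most IRs occurred when uric acid values were above 6 mg/dL", and that every anaphylaxis case except one at first dose followed a last value above 6. Section 7.2.2 states that "The risk of anaphylaxis and IRs is higher in patients who have lost therapeutic response". In a single-arm study whose other comparison is historical, IR risk by pre-infusion SUA is the most direct internal evidence bearing on that reasoning. The listed outputs would not show it.

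**Working it through.** **1. The plan's own figure.** Section 6.1.6 claims at least 90% power for 13% against 26% with 500 patients. Alpha and sidedness are not stated. I assume an exact one-sample binomial test at one-sided 0.025: reject at 110 or fewer events, exact alpha 0.0220, power above 99.9%. The claim holds as a lower bound; about 100 patients would already give 90.6%. Nothing below depends on it.

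**2. Item 3c against the protocol.** Inputs are the 14-day infusion interval and the 48-hour limit.
- Interval: 14 × 24 = 336 hours.
- Inside the limit: 48/336 = 14%. Outside it: 288/336 = 86%.
- Section 3.5.2.1 accepts a sample from anywhere in the interval. If several days means three or more (my reading), then 72 > 48, and every sample drawn as Section 3.6.1 directs is premature by the SAP's definition.
- The visit-day fallback sample always escapes the label. The standard route does not.

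The 86% is a share of hours, not of samples. The distribution of draw times is not given.

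**3. Item 4 against Section 3.5.5.** A full course of 26 infusions has 25 intervals. If each independently contains a permitted delay with probability q (assumed), the share of full-course patients open to the label is 1 − (1 − q)^25:

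| q | share |
|---|---|
| 1% | 22% |
| 2% | 40% |
| 5% | 72% |

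These figures show how quickly an untoleranced definition spreads. They are not the cells that will be reported, because 4a keeps only patients who also had an AE or SAE, and most patients are not expected to complete the course (about 500 of 1,500).

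**4. Search for an SUA-by-IR output in the SAP.**

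| SAP item | IRs | SUA level |
|---|---|---|
| Safety endpoints (by dose, by severity) | yes | no |
| 2c (IRs per total infusions) | yes | no |
| 3a, 3b | no | yes |
| 3c | yes | no, draw timing only |
| 24-week tables | listed | listed, not related |

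No row relates the two.

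**5. What the added table could show.** The number of infusions given after two high values is unknown, so I take m = 100 or 300, class risk p of 5% to 20%, and design effect DE of 1 to 2 (all assumed). Half-width = 1.96 × √(p(1 − p) × DE / m).
- m = 100: 1.96 × √(0.05 × 0.95 × 1/100) = 4.3 points, up to 1.96 × √(0.20 × 0.80 × 2/100) = 11.1 points.
- m = 300: 2.5 to 6.4 points.

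**The case against.** The strongest reply is that items 3c and 4a are not compliance rates. They count patients who carry the label and also had an event, so neither the 86% nor the 22% to 72% describes a planned output. That stands. A reader might infer that the report will overstate non-compliance by some such amount, and the documents do not support any figure.

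A reader might also infer that item 3b counts permitted conduct. Under the sentence requiring discontinuation, infusing after two consecutive high values is a violation, so 3b mostly captures real ones. The only gap is resumption after an interruption: the protocol does not say whether a high value then counts toward the two.

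It is tempting to follow the label further, into discontinuation from the study for a protocol violation (Section 3.5.6) or into the patients treated per protocol in SAP item 1f. The first concerns decisions during conduct, which a tabulation at reporting does not trigger. The second uses a term the SAP leaves undefined for that item. Both are conjecture.

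On the missing table, Section 3.2 promises data collection rather than an analysis, and the relationship is not a listed objective. The SAP is an outline without table shells. Also, if sites follow the rule, few infusions will come after two high values. These points make the table supportive rather than required. They do not remove the mismatch between a stated reason for collecting the data and the planned outputs.

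Finally, the SAP may want to know whether early draws miss a loss of response. That is a fair question, but it calls for a description of timing and not a violation heading.

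**Conclusion.** The point holds on the text. Item 3c labels samples drawn as the protocol directs, and item 4 does not exempt delays the protocol permits. The consequence is mislabelling within counts of patients who had events, and its size cannot be computed because draw times, delay frequency and event overlap are not given. Item 4 also catches genuine departures, such as dosing too early, so it needs an exemption rather than removal. No SAP item relates IRs to SUA level.

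The stated power is not in error, and the primary IR rate can be interpreted without the added table. The mixed wording on stopping is a secondary clarification. A reader might conclude that the stop must be made mandatory, but the study follows a label that says to consider stopping, and removing physician discretion is a trade-off for the sponsor. How often the two wordings would lead sites to act differently cannot be derived from the documents.

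**What to change.** 1. **Item 3c.** Replace it with a descriptive summary of draw-to-infusion time, or align it with the protocol's sampling window. Take it out of the violation heading.
2. **Item 4.** Exclude delays and interruptions recorded under Section 3.5.5 and state a tolerance for the two-week interval, for example ±3 days.
3. **New supportive table.** Give IR and anaphylaxis risk per infusion after the first, by the most recent on-treatment pre-infusion SUA values: both at or below 6, one above 6, both above 6, one value only or missing. Exclude screening and baseline values, because patients enter above 6 (Section 3.3.1). Flag infusions after an interruption. Use patient-clustered intervals (GEE or a patient-level bootstrap). Leave the one-event-per-patient primary summary unchanged.
4. **Item 3b.** Keep it, and show post-interruption resumptions separately.
5. **Stopping rule.** Clarify whether the stop is required or advised, and whether a post-interruption value counts toward the two. The choice is the sponsor's, and a wording change may need a protocol amendment.

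Items 1 to 4 cost edits to three SAP items plus one derivation and one table from data already collected. The comparison in the new table is observational: the class with both values above 6 holds only patients who were not stopped, and it may be small.
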